### 5.3 General Concomitant Medication and Supportive Care Guidelines

Because there is a potential for interaction of cabozantinib (XL184) with other concomitantly administered drugs through the cytochrome P450 system, the case report form must capture the concurrent use of all other drugs, over-the-counter medications, or alternative therapies. [Appendix III](#) is a sample participant information sheet about cabozantinib that can be presented to the participant.

Please refer to [Section 6.0](#) for supportive care guidelines associated with specific adverse reactions.

#### 5.3.1 Concomitant medications and therapies

##### 5.3.1.1 Anticancer therapy

If a participant requires additional systemic anticancer treatment, study treatment must be discontinued. Local intervention is discouraged unless medically unavoidable. Participants receiving local intervention (e.g.,

palliative radiation) are allowed to continue to receive study treatment at the investigator's discretion.

#### 5.3.1.2 Other medications

Participating participants MUST receive medically appropriate care and treatment for HIV infection, including antiretroviral medications when clinically indicated. Suspension or modification of an antiretroviral regimen during study participation will be permitted (after 8 weeks from study entry) at the discretion of the physician providing HIV care, provided the change and its rationale are carefully documented. However, due to potential differences in protocol therapy dosing associated with study stratification, therapeutic change to a ritonavir or cobicistat-containing antiretroviral regimen for a participant enrolled on a different study arm will necessitate immediate removal from the study.

Participants must be instructed to inform the investigators of the current or planned use or all other medications during the study (including prescription medications, over-the-counter medications, vitamins and herbal and nutritional supplements). It is the responsibility of the investigator to ensure that details regarding all medications are documented.

Bisphosphonates started prior to screening activities or initiated during the course of the study to control bone pain may be used with caution. **Please refer to [Section 6.1.15](#) for guidelines on prevention of osteonecrosis of the jaw (ONJ) when participants are receiving bisphosphonates.**

As the study will identify dose-limiting toxicities of this treatment regimen during the initial cycle of therapy, prophylactic growth factor (G-CSF) administration is not recommended. Based on observed toxicities, protocol-specified dose modification guidelines should be followed for subsequent therapy cycles. Management of anemia will be at the discretion of the treating physician,

No concurrent investigational agents are permitted.

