## PROTOCOL SYNOPSIS

**Title:** Phase I Trial of Cabozantinib (XL184) for Advanced Solid Tumors in Persons with HIV Infection

**Phase of Study:** Phase I

**Participating Institutions:** This protocol will be open to all AMC member sites.

**Accrual Target:** 16 to 42 participants

**Population:** Participants with incurable recurrent or metastatic solid tumors and HIV infection.

**Regimen:** This is a phase I, dose escalation study of cabozantinib (XL184) for advanced solid tumors in persons with HIV infection. Cabozantinib will be administered orally as a once daily dose continuously for 28-day cycles, according to the Protocol Schema. Participants will be stratified into three groups based on which HAART therapy they are receiving. The first group (**Stratum A**) will be participants on either ritonavir or cobicistat (potent CYP3A4 inhibitor)-containing antiretroviral therapy. Since a potential interaction leading to higher drug levels of cabozantinib in participants on ritonavir or cobicistat is expected, participants will be dose escalated, starting at ~33% of the standard dose (60 mg), using a classic 3 + 3 phase I clinical trial design. Dose increases will be in 20 mg increments to a maximum of 60 mg/day. The second group (**Stratum B**) will be participants being treated with either efavirenz or etravirine-containing regimens, in whom CYP3A4 induction may lead to lower levels of the study drug. These participants will be treated at the standard dose of cabozantinib, then dose escalated by 20 mg/cohort to a maximum of 100 mg/day in a 3 + 3 design. The third group (**Stratum C**) will include participants taking antiretrovirals not specified in Stratum A or B, or who are not receiving active antiretroviral therapy. These participants will be treated at the standard dose of 60 mg/day; no dose escalation is planned in this Stratum.

In this trial, a dose-limiting toxicity (DLT) will be defined as any cabozantinib-related grade 3 or 4 non-hematologic toxicity during the first cycle of therapy, including grade 3 nausea and/or vomiting and grade 3 diarrhea despite prophylaxis and/or treatment or any of the following grade 4 hematologic toxicities during the first cycle of therapy: thrombocytopenia, neutropenia of more than 5 days duration, and neutropenia of any duration with fever or documented infection; additionally, treatment delay of 14 days or greater during Cycle 1 due to unresolved toxicity or any

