## 5.0 TREATMENT PLAN

### 5.1 Agent Administration

Treatment will be administered on an outpatient basis. Reported adverse events and potential risks are described in [Section 7.0](#). Appropriate dose modifications are described in [Section 6.0](#). No investigational or commercial agents or therapies other than those described below may be administered with the intent to treat the participant's malignancy.

Cabozantinib will be administered orally as once daily doses continuously over 28 day cycles in each of three treatment strata in participant cohorts as detailed in the table below. The starting dose in each treatment Stratum will be Dose Level 1. Dose escalation will proceed in participant cohorts within each Stratum according to the scheme described in [Section 5.2](#).

**NOTES: The participant will be requested to maintain a medication diary of each dose of medication. The medication diary will be returned to clinic staff at the end of each course.**

**The site will be required to document study agent return by participant in source documents. Non-compliance with study agent administration should be noted at the time of diary collection and the participant should be instructed again regarding dosing instructions.**

**Missed cabozantinib doses will NOT be made up. Participants who have missed a dose should wait until the next scheduled dose to resume therapy.**

For Stratum A, one dose de-escalation cohort (Dose Level -1) will be permitted for excessive toxicity observed at the initial (Dose Level 1) cohort. For Stratum B and Stratum C, two dose de-escalation cohorts (up to Dose Level -2) will be permitted for toxicity observed at initial cohorts.

For participants treated on Stratum A no dose escalation will proceed beyond Dose Level 3 (60 mg). For participants treated on Stratum B, no dose escalation will proceed beyond Dose Level 2 (100 mg). For participants treated on Stratum C, no dose escalation will proceed beyond Dose Level 1.

Dose Escalation Schedule			
Dose Level	Dose of Cabozantinib (XL184)*		
	Stratum A ART Regimens Including Drugs that Inhibit CYP3A4 A (mg/day)	Stratum B ART Regimens Including Drugs that Induce CYP3A4 B (mg/day)	Stratum C All Other ART Regimens C (mg/day)
Level -2	-	20	20
Level -1	20 mg every other day	40	40
Level 1	20	60	60
Level 2	40	100	-
Level 3	60	-	-

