#### **5.4 Duration of Therapy**

In the absence of treatment delays due to adverse event(s), treatment may continue until one of the following criteria applies:

- Disease progression,
- Intercurrent illness that prevents further administration of treatment,
- Dose-limiting toxicity (DLT requiring discontinuation of therapy, as defined in [Section 5.2](#)). Dose reductions in the first cycle of therapy for cabozantinib-related adverse events are permitted.
- Other unacceptable adverse event(s),
- Treatment delay of 14 days or greater during Cycle 1 due to unresolved toxicity (DLT definition, [Section 5.2](#)).
- Treatment delay in subsequent cycles > 6 weeks due to toxicity (treatment delays for other reasons may be permitted at the discretion of the Study Chairs),
- Participant decides to withdraw from the study.
- General or specific changes in the participant's condition render the participant unacceptable for further treatment in the judgment of the investigator, including:
  - Necessity for treatment with other anticancer treatment prohibited by the protocol.
  - Change to a ritonavir or cobicistat-containing antiretroviral regimen for a participant enrolled on a different study arm (see [Section 5.3.1.2](#)).
  - Sexually active participants who refuse to use medically accepted barrier methods of contraception (e.g., male condom, female condom) during the course of the study and for 6 months following discontinuation of study treatment.
  - Women who become pregnant or are breastfeeding.
- Request by regulatory agencies for termination of treatment of an individual participant or all participants under the protocol.
- Significant noncompliance with the protocol schedule in the opinion of the investigator.
- The minimum dose of study treatment for Stratum A will be the Dose Level -1 dose, and the lowest dose of study treatment for Stratum B and Stratum C will be the Dose Level -2 dose. Participants who cannot tolerate the lowest Dose Level dose for the specified study Stratum will have study treatment discontinued.

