## 6.0 DOSING DELAYS/DOSE MODIFICATIONS

### Dose modifications for Cabozantinib (XL184)

Toxicities warranting treatment delays and dose modifications, along with supportive care guidelines, are noted below.

Stratum-based dose de-escalation of cabozantinib will be permitted for participants experiencing specified toxicity when treated at a particular dose level, as noted below; reductions will be at one-dose-level increments. In no case will dose de-escalation occur beyond the lowest specified Dose Level dose for a particular Stratum (Dose Level -1 for Stratum A; Dose Level -2 for Stratum B and Stratum C). Dose reductions are permanent. No intra-participant dose escalation will be permitted.

**NOTE: Dose modification during Cycle 1 WILL be permitted.** Participants will be permitted to continue study therapy provided no other criteria for protocol discontinuation apply ([Section 5.4](#)). **HOWEVER, treatment delay of 14 days or longer due to unresolved toxicity during Cycle 1 will require discontinuation of study treatment** ([Section 5.4](#)).

**NOTE:** If a participant experiences several adverse events and there are conflicting recommendations, the investigator should use the recommended dose adjustment that reduces the dose to the lowest level.

**NOTE:** Starting in Cycle 2, if toxicity requiring treatment delay does not resolve in less than or equal to 6 weeks, the study treatment will be discontinued. Treatment delays for other reasons may be permitted at the discretion of the Study Chairs.

Dose De-Escalation Schedule			
Dose Level	Dose of Cabozantinib (XL184)*		
	Stratum A ART Regimens Including Drugs that Inhibit CYP3A4 A (mg/day)	Stratum B ART Regimens Including Drugs that Induce CYP3A4 B (mg/day)	Stratum C All Other ART Regimens C (mg/day)
Level -2	-	20	20
Level -1	20 mg every other day	40	40
Level 1	20	60	60
Level 2	40	100	-
Level 3	60	-	-

\* Cabozantinib (XL184) must be taken whole and on an empty stomach. Participants must fast for 2 hours before and 1 hour following each dose of cabozantinib (XL184). To permit pharmacokinetic sampling studies, AM dosing is required during the first cycle of therapy.

AStratum A: Participants taking either ritonavir-boosted or cobicistat-boosted ART regimens

BStratum B: Participants taking either efavirenz or etravirine-based ART regimens.

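### Stopping efavirenz or etravirine after week 8 triggers no required action, so a Stratum B participant may stay on 100 mg, 1.67 times the highest dose planned without an inducer

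*Combined protocol and SAP*

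**What the plan says.** **ART changes.** Section 5.3.1.2 allows the regimen to be suspended or modified after eight weeks from entry, at the discretion of the physician providing HIV care, with the change and its reason documented. One change is singled out: "therapeutic change to a ritonavir or cobicistat-containing antiretroviral regimen for a participant enrolled on a different study arm will necessitate immediate removal" from the study. The reason given is "due to potential differences in protocol therapy dosing associated with study stratification". The matching discontinuation criterion in Section 5.4 is "Change to a ritonavir or cobicistat-containing antiretroviral regimen for a participant enrolled on a different study arm". Stopping an inducer appears in neither place.

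**Doses.** Section 5.1 caps Stratum B at 100 mg and Stratum A at 60 mg. For the stratum without inducer or booster, "For participants treated on Stratum C, no dose escalation will proceed beyond Dose Level 1", which is 60 mg. The Synopsis describes Stratum B participants as those "in whom CYP3A4 induction may lead to lower levels of the study drug".

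**Dose reduction.** Section 6.0 says "Stratum-based dose de-escalation of cabozantinib will be permitted for participants experiencing specified toxicity when treated at a particular dose level", one level at a time, and "Dose reductions are permanent". A note to Table 6-1 extends this to milder toxicity after Cycle 1.

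**Other relevant text.** Section 5.3.1.3, repeated in 8.1.1, advises caution when a strong CYP3A4 inducer is stopped in a patient on stable cabozantinib, because exposure could rise significantly. Section 5.4 lets the investigator stop treatment on general clinical judgment.

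**The concern.** The stated reason for the removal rule is that dose depends on stratum. That reason applies equally to a participant who leaves Stratum B conditions by dropping the inducer, but the trigger covers only the addition of a booster. Someone who stops efavirenz or etravirine, and either takes an unboosted regimen of other agents or no ART, meets the description of Stratum C while holding a dose that Stratum C is never given.

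What is at stake is the safety of individuals in later cycles. The protocol itself calls the exposure rise potentially significant, yet gives sites no defined response and no stated basis for lowering the dose before toxicity appears. From Cycle 3 the scheduled visits fall on Day 1 of each 28-day cycle (Section 9.2). No PK sample is triggered by an ART change. Treatment may continue indefinitely.

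**Working it through.** The plan gives no figure of its own on this point, so the check traces the rule and then sizes the gap.

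**1. What each provision requires when a Stratum B participant on 100 mg stops the inducer without starting a booster**

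| Provision | Applies? | Action required |
|---|---|---|
| 5.3.1.2 and 5.4, ART trigger | No, booster only | None |
| 5.3.1.3 caution | Yes, if efavirenz or etravirine counts as a strong inducer | None specified |
| 6.0 and Table 6-1 | Only once there is toxicity | None before toxicity |
| 5.4 investigator judgment | Yes | Optional stop; no provision to lower the dose |

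Staying on 100 mg is therefore permitted, though not required.

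**2. Dose against this trial's cap without an inducer.** Inputs: 100 mg (Stratum B) and 60 mg (Stratum C), both from Section 5.1. Ratio = 100/60 = 1.67.

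**3. Rise over the participant's own earlier exposure.** If the inducer cuts AUC by a fraction r and exposure is proportional to dose, stopping it multiplies exposure by 1/(1 − r). The documents give no r for efavirenz or etravirine, so r is an assumption. The only inducer figure is 77% for rifampin (5.3.1.3).

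- r = 20%: 1/0.80 = 1.25
- r = 40%: 1/0.60 = 1.67
- r = 60%: 1/0.40 = 2.5
- r = 77%: 1/0.23 = 4.35

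Whatever r is, the end point is 100 mg without induction, so the 1.67 in step 2 does not depend on it. Section 5.3.1.3 also lists efavirenz as an MRP2 inhibitor, which may partly offset its induction.

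**4. Against earlier experience.** Section 2.4 gives a capsule MTD of about 138 mg freebase; Section 8.1.1 states this trial's tablets as freebase. 100/138 = 0.72. Applying the 15% and 19% higher tablet AUC point estimates in Section 2.4 (reported there as not statistically different), 100 × 1.15/138 = 0.83 and 100 × 1.19/138 = 0.86. The dose stays below the MTD on each basis.

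**5. Against the switches the rule does catch.** Assume a booster acts like ketoconazole (+38%, 5.3.1.3); no booster figure is given.

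- Stratum C, 60 mg plus booster: 60 × 1.38 = 82.8 mg-equivalent; removed.
- Stratum B, 100 mg, booster replacing the inducer: 100 × 1.38 = 138 mg-equivalent; removed.
- Stratum B, 100 mg, inducer simply stopped: 100 mg-equivalent; no action.

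The uncovered case lies between the two covered ones. It exceeds the first by 100/82.8 = 1.21 times, unless the true booster effect is above 100/60 − 1 = 67%.

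**6. Timing.** Enrollment is at most one week before treatment starts (Section 4.1), so eight weeks from entry is no earlier than about 56 − 7 = 49 days into treatment. Cycle 1 ends at day 28. The DLT window and the scheduled Day 22/23 PK precede any permitted change.

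**7. Numbers exposed.** Section 12.2 allows the MTD level in a stratum to expand to 6 to 12, so at most about 12 participants could be on 100 mg. The switching rate is not given. Section 3.1.9 requires a stable regimen at entry with no intention to change it within eight weeks.

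**The case against.** The strongest reply is that the risk was seen and left to clinical judgment. The caution in 5.3.1.3 directly follows a sentence on antiretrovirals that are strong inducers or inhibitors, and that sentence points to 3.2.10, where efavirenz and etravirine are named. ART changes must be documented, toxicity can prompt reduction even at low grade after Cycle 1, and the investigator may stop treatment. Treating an added booster more strictly than a lost inducer is also defensible: Stratum A starts at about a third of the standard dose, and 100 mg plus a booster would come to roughly the earlier MTD on the ketoconazole assumption, while 100 mg alone would not.

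Much of this stands. It rules out saying that the protocol overlooked the hazard or that the booster rule is misconceived. It does not close the gap: a caution without an action leaves sites to improvise, and the obvious response, a pre-emptive step down to 60 mg, has no stated basis in 6.0.

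Three stronger readings are tempting and should not be drawn.

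- *That 100 mg without an inducer is shown to be unsafe.* The 60 mg in Stratum C is the standard dose with no escalation planned; the documents do not present it as a toxicity ceiling, and earlier single-agent studies started at 100, 125 and 175 mg.
- *That the related serious events in the earlier phase II study starting at 100 mg (92 of 531 subjects, seven fatal) measure the excess risk.* There is no 60 mg comparator, and the study summary does not say whether its 100 mg was salt or freebase.
- *That the excess could readily be 2.5- or 5-fold.* Those ratios (100/40 and 100/20) need Stratum C to fail 60 mg, and then 40 mg, while Stratum B tolerates 100 mg. Only 1.67 follows from the planned doses.

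**Conclusion.** The point holds as a modest safety gap. After week 8 a Stratum B participant may stop the inducer and remain on 1.67 times the highest dose this trial plans without one, with no required response. The ratio rests only on the planned doses; any statement about exposure needs dose proportionality, and the rise from the participant's own earlier level cannot be sized without an induction figure.

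The gap opens only if Stratum B reaches 100 mg, the participant is still on that dose after week 8, and the new regimen has no booster. A reader might infer that the MTD or the main PK comparison is compromised; the timing in step 6 shows that neither is. The reason to act is that the hazard is foreseeable, the protocol names it, and the remedy is small.

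**What to change.** In Sections 5.3.1.2 and 5.4, state that a Stratum B participant above 60 mg/day who stops efavirenz or etravirine without starting ritonavir or cobicistat must either be reduced to 60 mg/day or be removed from study treatment. Because "For Stratum B and Stratum C, two dose de-escalation cohorts (up to Dose Level -2) will be permitted for toxicity observed at initial cohorts", add that if Stratum C has formally de-escalated, the target is the Stratum C dose level then open. Naming an open level avoids relying on a tolerated Stratum C dose that may not yet be established mid-trial.

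In Section 6.0, state that this reduction is allowed without toxicity and, where Stratum C has de-escalated, may cross more than one level. All the target doses (60, 40 and 20 mg) are already Stratum B levels, and 100 to 60 mg is a single step in the Section 5.1 table.

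The cost is wording in three sections. The clinical downside is that a few participants who might have tolerated 100 mg are reduced or removed, and under 6.0 the reduction stays in force even if the inducer is restarted.

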#### 5.3.1.3 Potential drug interactions

CYP450 isozymes:

*In vitro*, XL184 is a substrate of CYP3A4 and a weak substrate of CYP2C9. In healthy volunteers, XL184 AUC increased 38% with co-administration of ketoconazole, a strong inhibitor of CYP3A4, and decreased by 77% with a strong CYP3A4 inducer rifampin. Therefore, avoid chronic use of strong CYP3A4 inducers such as rifampin, dexamethasone, phenytoin, carbamazepine, rifabutin, rifampentin, phenobarbital, and St. John's Wort while taking XL184. Avoid chronic use of strong CYP3A4 inhibitors such as ketoconazole, itraconazole, clarithromycin, indinavir, nefazodone, nelfinavir, and ritonavir. Use alternative medications. **Use of antiretroviral agents that are strong**

**inducers or inhibitors of CYP3A4 are permitted as per exclusion criteria 3.2.10 and 3.2.11.**

[**Note:** Use caution when discontinuing medication that is a strong inducer of CYP3A4 in patients who has been on a stable dose of XL184, as this could significantly increase the exposure to XL184.]

XL184 is a noncompetitive inhibitor of CYP2C8 ( $K_{iapp} = 4.6 \mu M$ ), a mixed-type inhibitor of both CYP2C9 ( $K_{iapp} = 10.4 \mu M$ ) and CYP2C19 ( $K_{iapp} = 28.8 \mu M$ ), and a weak competitive inhibitor of CYP3A4 (estimated  $K_{iapp} = 282 \mu M$ ) in human liver microsomal (HLM).  $IC_{50}$  values  $>20 \mu M$  were observed for CYP1A2, CYP2D6, and CYP3A4 isozymes. XL184 is an inducer of CYP1A1 mRNA in human hepatocyte incubations,

Avoid grapefruit/ grapefruit juice and Seville oranges while participating in this trial.

#### P-glycoprotein/ MRP2:

*In vitro* data indicate that XL184 is an inhibitor of P-glycoprotein transport activity ( $IC_{50} = 7.0 \mu M$ ). Co-administration of XL184 with a P-gp substrate may result in an increase in P-gp substrate plasma concentration. Therefore, use caution when administering XL184 with drugs known to be P-gp substrates (e.g., fexofenadine, aliskiren, ambrisentan, digoxin, colchicine, maraviroc, posaconazole, tolvaptan, etc.).

XL184 is also a substrate of drug transporter MRP2, which may result in an increase plasma concentration of XL184 when administered with an inhibitor of MRP2. Use caution and monitor adverse events when administering XL184 with MRP2 inhibitors such as cyclosporine, delavirdine, efavirenz, emtricitabine.

